3.6.1. Temporary Discontinuation of Study Drug Treatment

Temporary discontinuation is defined as missing of more than 3 consecutive doses of the study drug. Skipping 14 or more consecutive doses of study drug will be considered a major protocol violation.

The reasons for temporary study drug discontinuation should be recorded in the appropriate section of the study drug dispensing and compliance log in the electronic Case Report Form (eCRF).

The subject will report any temporary discontinuation to the investigator and will be instructed by the investigator regarding continuation of treatment.

3.6.2. Early Termination (ET)

An ET visit should be completed for all patients who prematurely terminate treatment or who become pregnant (see Section 3.11.4 for details of procedures).

Early termination refers to the study drug termination and not termination of the patient from the study. Patients will be asked to continue all scheduled visits and safety assessments after study drug discontinuation (with the exception of drug dispensing and accountability, pregnancy testing, and pharmacokinetic sampling).

Patients in the 1.5 mg/day (high dose) treatment arm, whose treatment with laquinimod was discontinued, were invited to attend an early termination visit (to return study medication and perform drug accountability). At this visit, only safety assessments were to be completed. These included vital signs, clinical laboratory tests, pregnancy test, adverse event inquiry, drug accountability, review of concomitant medication, and C-SSRS (see also Section 3.11.3.1.5). Patients were asked to continue scheduled follow up safety visits per the current schedule.

Women of child bearing potential should continue using 2 acceptable contraception methods up to 30 days after the last dose of study medication has been administered.

Moderate/strong CYP3A4 inhibitors are disallowed during the 30 days after the last laquinimod dose has been administered (see [Appendix B](#)).

Plasma levels of drugs that are CYP1A2 substrates may decrease when combined with laquinimod and within 30 days after the last laquinimod dose, rendering these drugs less effective (see [Appendix C](#)).

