3.11.3.1.5. Month 12 (Visit 8) –or Early Termination

The following procedures/assessments will be performed at Month 12 (Visit 8) or early termination:

- Review of concomitant medications
- Adverse events inquiry
- perform full physical examination (including weight)
- perform vital signs measurements
- perform single ECG
- perform clinical laboratory tests
- estimated creatinine clearance calculation
- clinical hematology
- lipid profile
- thyroid function (T3, T4, TSH)

- blood sample for soluble biomarkers (cytokines)
- blood sample for gene expression analysis
- blood sample for monocyte analysis (**Only at selected sites in a subgroup of patients**)
 - Blood sample for monocyte collection and analysis has to be done in accordance with the laboratory manual
 - For UK patients, the sample can be drawn prior to the Month 12 visit, as it coincides with the PET scan visits
- serum β -HCG in women of child-bearing potential
- urine β -HCG in women of child-bearing potential
- additional urine β -HCG in women of child-bearing potential at PET facilities (**Only in a subgroup of patients**)
- Ascertaining use of acceptable contraception
- PK drug concentration sampling
- C-SSRS (since last visit version)
- MRI scan
 - If anxiolysis is required in order to perform the MRI scan, the scan should be performed at the end of the study visit day.
- MRS scan (**Only at selected sites in a subgroup of patients**)
- PET scan (**Only in a subgroup of patients**)
 - The PET scan can be done 2 to 5 weeks prior to the Month 12 visit.
 - Patients taking benzodiazepines should be instructed to stop taking them for 3 days prior to having the PET scan.
- UHDRS-TMS
- UHDRS-TFC
- UHDRS-FA
- mPPT
- PBA-s
- CIBIC-plus
- HD-QoL
- EQ-5D-5L
- WLQ
- Q-Motor assessments
- HD-CAB
 - Includes Symbol Digit Modalities Test (SDMT), Emotion Recognition, Trail Making Test, Hopkins Verbal Learning Test, revised (HVLRT-R), Paced Tapping at 3 Hz, One Touch Stockings of Cambridge (OTS, abbreviated 10 trial version)
- CDR-SB
- HADS
- Review study compliance
- Study drug collection and reconciliation

Moderate/strong CYP3A4 inhibitors are disallowed during the 30 days after the last laquinimod dose has been administered (see [Appendix B](#)).

Plasma levels of drugs that are CYP1A2 substrates may decrease when combined with laquinimod and within 30 days after the last laquinimod dose, rendering these drugs less effective (see [Appendix C](#)).

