3.11.4. Procedures After Study Drug Treatment

3.11.4.1. Follow-Up (Week 56, Visit 9)

The following procedures/assessments will be performed at the follow up visit (Week 56, Visit 9):

- Review of concomitant medications
- Adverse events inquiry
- perform clinical laboratory tests
- estimated creatinine clearance calculation
- clinical hematology
- perform full physical examination (including weight)
- perform vital signs measurements
- perform single ECG
- serum β -HCG in women of child-bearing potential
- urine β -HCG in women of child-bearing potential
- Ascertaining use of acceptable contraception
- C-SSRS (since last visit version)

Patients who participate in the study in compliance with the protocol for the entire duration of the double-blind treatment will be considered to have completed the study.

For patients who complete the study or withdraw prematurely, final evaluations will be performed at the end-of-treatment visit or as soon as possible thereafter. Procedures for patients who withdraw prematurely from the study are described in Section [4.3](#).

If it is not possible to schedule the ET visit within 2 weeks after end of treatment, only the safety evaluations for that visit (vital signs, clinical laboratory tests, pregnancy test, adverse event

inquiry, drug accountability, review of concomitant medication, and C-SSRS, see Section 3.6.2) need to be performed.

Patients with ongoing adverse events or clinically significant abnormal laboratory test results (as interpreted by the investigator) will be monitored as described in Section 7.1.2 and Section 7.3, respectively.

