7.2. Pregnancy

To further emphasize the importance of use of acceptable contraception and avoidance of pregnancy under laquinimod exposure, and to reduce as much as possible the exposure to laquinimod if a pregnancy occurs despite all recommended measures, all women of child-bearing potential (for example women who are not postmenopausal or have not undergone surgical sterilization) and not using acceptable methods of contraception, will be instructed about the teratogenicity and potential delayed risks for a child exposed in utero to laquinimod. These subjects will be counseled about the importance of using 2 acceptable methods of contraception throughout the entire study duration and until 30 days after the last dose of treatment was administered and about the need to stop treatment immediately if pregnancy is suspected. Patients who are women of child-bearing potential must use 2 acceptable methods of contraception for 30 days prior to initiation of treatment, throughout treatment duration and until 30 days after the last dose of treatment.

Acceptable methods of birth control include: Intrauterine devices, barrier methods (condom or diaphragm with spermicide) and hormonal methods of birth control (oral contraceptive, contraceptive patch, long-acting injectable contraceptive).

The patients' understanding of the importance of preventive pregnancy measures and their ability to follow the required instructions will be ensured by the investigator.

Additionally, monthly pregnancy tests (urine dipstick and/or serum pregnancy β -hCG test, as applicable per the relevant time point) will be performed. Early terminated subjects who are in the study for the purpose of follow-up will not be required to take the pregnancy tests if the last study drug dose was taken more than 30 days prior to the visit.

All pregnancies of women participating in study and that occur during the study, or within 30 days after the last dose of treatment was administered, are to be reported immediately to the individual identified in the clinical study personnel contact information section of this protocol, and the investigator must provide the LSO/CRO with the pregnancy form. The process for reporting a pregnancy is the same as that for reporting a serious adverse event (see Section 7.1.5.3).

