7.3.6. Human Chorionic Gonadotrophin Tests

Human chorionic gonadotropin (β -hCG) serum test will be performed for all women of child-bearing potential (women who are not post menopausal or who have not undergone surgical sterilization) at screening (Visit 1) and at all subsequent study visits. Age-appropriate normal ranges for HCG should be used. If the reading for the serum pregnancy test is indeterminate, the test should be repeated after 3-4 days to see whether there is an increase in β -hCG or whether it is a stable elevation. If no increase is observed, the patient will not be considered to be pregnant. However, no study drug will be administered until this is resolved.

Urine β -hCG tests will be performed for all women of child-bearing potential at baseline (Visit 2), and at all subsequent visits, and if clinically indicated at any other time.

In addition, starting after Visit 3, a urine β -hCG test will be performed in women of child-bearing potential every 28 (\pm 2) days, by the patient at home, and recorded in the patient's medical records. The patient will be contacted by telephone within 72 hours after the scheduled test is to be performed and asked specific questions regarding the test. In case of suspected pregnancy (positive urine β -hCG test result), absence of menstruation or any other reason suggesting pregnancy, the caller will make sure that the study drug has been discontinued and the subject will be instructed to arrive to the site as soon as possible (within 10 days) with all remaining study drugs capsules.

Any patient who becomes pregnant during the study will be withdrawn. Procedures for reporting the pregnancy are provided in Section 7.2.

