2. At each scheduled visit, female subjects of childbearing potential (women who are not post menopausal or who have not undergone surgical sterilization) will undergo a urine β -hCG test. In addition, a serum pregnancy β -hCG test will be performed at each visit.
 - a. In case the the urine test is negative, study drugs will be dispensed according to planned visit tasks (see [Table 3](#)).
 - i. If the blood test is positive the subject will be contacted immediately and instructed to stop taking the study drug. The subject should be invited to attend an ETD visit.
 - ii. If the blood test is negative – study procedures will be undertaken as planned.
 - b. In case the urine test is positive – the study drug will not be dispensed (if this occurs at baseline visit, the subject will not be eligible to participate in the study and will be considered as a screening failure)
 - iii. If the blood test is positive, the subject will be invited to the site for an ETD visit
 - iv. If the blood test is negative, the subject will be contacted and informed about the test result and the study drugs will be sent to her by courier as soon as possible.

In case of an established diagnosis of pregnancy, the Treating Physician/Neurologist should discuss with the subject the possible risk to the fetus, including the possibility of termination of the pregnancy. Subjects who become pregnant will be monitored for the outcome of the pregnancy (including spontaneous or voluntary termination). If the pregnancy continues to term, the outcome (health of the infant up to 8 weeks of age), details of birth, and presence or absence of any birth defect, congenital abnormalities, or maternal and newborn complications, will be reported to the sponsor. Any complication of pregnancy during the study and any complication of pregnancy that the investigator becomes aware of after termination from the study will be reported as an adverse event or serious adverse event, as appropriate.

1. Starting from Visit 3 (Month 1), the following actions will be taken:
 - a. The subject will be provided with home pregnancy urine β -hCG test kits and will be guided how to perform the test.
 - b. The subject will be instructed to perform the test in monthly intervals (every 28 (\pm 2) days) from the visit date. These dates should be recorded by the study coordinator and a telephone call, will be scheduled to be performed within 72 hours of the urine test date.

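### Section 3.6.2 drops pregnancy testing after early drug discontinuation with no time limit, but Section 7.2 waives it only beyond 30 days from the last dose

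*Protocol*

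**What the plan says.** Section 3.6.2 (Early Termination) explains that early termination means stopping drug, not leaving the study. Patients are asked to continue scheduled visits and safety assessments "with the exception of drug dispensing and accountability, pregnancy testing, and pharmacokinetic sampling". The same section adds: "Women of child bearing potential should continue using 2 acceptable contraception methods up to 30 days after the last dose of study medication".

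Section 7.2 (Pregnancy) calls for monthly pregnancy tests. It then says that early-terminated subjects who remain for follow-up need not take the "pregnancy tests if the last study drug dose was taken more than 30 days prior to the visit". It also requires immediate reporting of pregnancies "that occur during the study, or within 30 days after the last dose of treatment was administered".

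Two other places give the general schedule. Section 7.3.6 places the serum test "at screening (Visit 1) and at all subsequent study visits", and adds a urine test at home every 28 (±2) days, starting after Visit 3. Appendix A, item 5, has a sentence that begins "At each scheduled visit, female subjects of childbearing potential" and calls for urine and serum tests. It counts the home-test interval from the visit date.

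The early termination visit itself is covered. Section 3.11.3.1.5 lists serum and urine hCG among the procedures that "will be performed at Month 12 (Visit 8) or early termination". Section 3.11.4.1 keeps a pregnancy test even in the reduced safety set that applies "If it is not possible to schedule the ET visit within 2 weeks after end of treatment".

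**The concern.** A site looking up what continues after a woman stops drug will turn to Section 3.6.2, because that is its subject. Read as written, it removes pregnancy testing from that point on. The pregnancy section removes it only after 30 days.

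The first 30 days are the period the protocol treats as still at risk. Two contraceptive methods remain mandatory and pregnancies must be reported at once. Section 1.4.1.3.1 says that exposure in pregnancy must be avoided and cites malformations in rats at doses similar to 0.5 mg/day in humans. A site that follows Section 3.6.2 would omit a test that Section 7.2 still requires, and a pregnancy in that window could be found and reported later than intended.

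**Working it through.** There is no planned figure to reproduce. The check sets the two rules side by side and applies them to the visit schedule in Table 3.

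**The rules**

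| Time since last dose | Section 3.6.2 | Section 7.2 |
|---|---|---|
| 30 days or less | no test | test |
| more than 30 days | no test | no test |

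They disagree in the first row only.

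**A stop between clinic visits.** Inputs: last dose at Week 23 (chosen for illustration); Visit 6 at Week 26 with a ±7-day window; Visit 7 at Week 39.
- Visit 6: (26 − 23) × 7 = 21 days after the last dose. The window gives 21 − 7 = 14 to 21 + 7 = 28 days, all within 30. Section 3.6.2 exempts and Section 7.2 requires.
- Visit 7: (39 − 23) × 7 = 112 days. Both sections exempt.

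A clinic-visit conflict therefore needs a scheduled visit that follows the early termination visit and falls within 30 days of the last dose.

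**A stop at a scheduled clinic visit.** Gaps to the next clinic visit:
- Week 4 to 13: (13 − 4) × 7 = 63 days.
- Week 13 to 26, 26 to 39 and 39 to 52: 13 × 7 = 91 days each.

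No later clinic visit falls within 30 days, so clinic visits alone show no conflict. The home test can still fall in the window. If the last dose is at the Week 26 visit and the interval runs from that date, the next home test is due at 28 − 2 = 26 to 28 + 2 = 30 days. None of these is more than 30 days, so Section 7.2 does not waive the test, while Section 3.6.2 excepts pregnancy testing without distinguishing clinic from home. This step assumes that Section 7.2's monthly tests include the home tests. That is the natural reading, because the waiver directly follows the sentence about monthly testing, although its limit is worded in terms of a visit.

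**Completers, for comparison.** Visit 9 includes serum and urine hCG. With a last dose at Week 52 it falls at (56 − 52) × 7 = 28 days. The protocol thus plans a test late in the same 30-day window for women who finish treatment.

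**The case against.** The best reply is that Section 7.2 already settles the matter. It sits in the pregnancy section, names exactly this group of women and gives the rule. The parenthesis in Section 3.6.2 can be read as listing which procedures lapse, with Section 7.2 saying when. Several safeguards also stand: hCG at the early termination visit, contraception to day 30, immediate reporting of pregnancies, and urine testing at any time if clinically indicated (Section 7.3.6).

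The safeguards limit the harm, and that part of the reply is accepted. The reading that Section 7.2 governs is reasonable, but nothing in the protocol says so. Section 3.6.2 is the section dedicated to early termination, it carries no time limit, and it does not refer to Section 7.2.

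Three stronger readings should be resisted.
- A reader might see Section 7.3.6 and Appendix A, item 5, as further contradictions because they mention no waiver. They are general schedules that the specific rule in Section 7.2 qualifies. Much of the Appendix A scheme concerns whether to dispense drug, which does not arise for a woman already off it.
- A reader might count every day from the early termination test to day 30 as untested because of Section 3.6.2. Section 7.2 does not call for testing on each of those days. What Section 3.6.2 removes is whichever clinic or home tests happen to fall in the window.
- A reader might infer continued dosing in pregnancy. The conflict arises only after drug has stopped.

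**Conclusion.** The contradiction holds in current text and is confined to Sections 3.6.2 and 7.2 within 30 days of the last dose. It affects women of child-bearing potential who stop drug early and then have a clinic visit or, on the reading of monthly testing set out above, a home test due in that period. Women who stop at a scheduled visit are not exempt from the problem, because the home test can be due at days 26 to 30.

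The effect is possible later detection and reporting of a pregnancy. It does not touch dosing, the efficacy endpoints or their analysis. The number of women affected cannot be derived, since the protocol gives neither the number of women of child-bearing potential nor the timing of discontinuations. The severity is minor. This is an inconsistency of wording, not a questionable design choice: the 30-day rule in Section 7.2 is sound and needs only to be carried into Section 3.6.2.

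**What to change.** In Section 3.6.2, replace the words *pregnancy testing* in the list of exceptions with *pregnancy testing more than 30 days after the last dose (see Section 7.2)*. Because this counts from the last dose and does not depend on a visit, it covers home tests as well as clinic tests.

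A cross-reference to Section 7.2 in Section 7.3.6 and in Appendix A, item 5, would help sites but is optional.

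The cost is one phrase. No visit, contact or procedure is added: the clinic visits and the home tests are already scheduled, and Section 7.2 already calls for testing in this period.

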3.7. Study Drug Supply and Accountability

3.7.1. Study Drug Storage and Security

Laquinimod and matching placebo capsules must be stored at room temperature (15-25°C), in a dry place, and in a securely locked, substantially constructed cabinet or enclosure. Only authorized personnel will have access to the study drug. The study site personnel at each site will be responsible for correct storage and handling of the study drug. Maintenance of a temperature log (manual or automated) is required and should be available for review by the monitor for the duration of the study. The temperature shall be recorded daily and the max/min thermometer reset after each reading. Complete instructions on receipt, storage, and handling of study drugs will be detailed in the Pharmacy Manual.

3.7.2. Study Drug Accountability

Each study drug shipment will include a packing slip, listing the contents of the shipment and any applicable forms.

The investigator is responsible for ensuring that deliveries of study drug and other study materials from the sponsor are correctly received and recorded, handled and stored safely and properly in accordance with the local regulations, and used in accordance with this protocol. Study drugs accountability records must be maintained at the site at all times.

During the study, all used and unused study drugs and the corresponding accountability forms must be returned by the monitor to the sponsor or sponsor's designee on an on-going basis for reconciliation and destruction, with account given for any discrepancies. A photocopy of these records must be kept at the study sites.

The accountability of the returned study drugs should be performed and recorded by the sponsor's assigned monitor. The Subject Number, the date, batch code/batch number, pack number and quantity of study drugs returned by the subject will be checked for correctness and recorded on the appropriate accountability forms, to be provided by the sponsor.

The monitor will use the IRT to record the returns.

3.8. Maintenance of Randomization and Blinding

The randomization code will be maintained by the CSC department. At the time of analysis, when treatment codes are revealed, the CSC department will provide the randomization code to the statistician assigned to this study.

Staff responsible for bioanalysis and pharmacokinetic data analysis will not have access to any clinical data and will provide concentration data to other staff members in a blinded manner (i.e., a dummy subject identifier will be linked to an individual subject's concentration data).

For information about personnel who may be aware of treatment assignments, see Section 3.3. These individuals will not be involved in conduct of any study procedures or assessment of any adverse events.

For a serious adverse event considered related and unexpected (ie, reasonable possibility; see Section 7.1.4) to the study drug, the sponsor's Global Patient Safety & Pharmacovigilance

Department may independently request that the treatment code be revealed (on a case-by-case basis). If this occurs, the investigator will remain blinded to treatment.

In case of a serious adverse event, pregnancy, or in cases when knowledge of the study drug assignment is needed to make treatment decisions, the investigator may unblind the patient's drug assignment as deemed necessary, mainly in emergency situations. Individual treatment codes, indicating the treatment randomization for each randomized patient, will be available to the investigator(s) and/or pharmacist(s) at the study center via the IRT, both via telephone and internet.

If possible, the sponsor should be notified of the event prior to breaking of the code. If this is not possible, the sponsor should be notified immediately afterwards, and the patient's drug code assignment should not be revealed. Breaking of the treatment code can always be performed by the site without prior approval by the sponsor.

The circumstances leading to the breaking of the code should be fully documented, in the investigator's study files and in the patient's source documentation. Treatment assignment should not be recorded in any study documents or source document.

In blinded studies, for adverse events that are defined as: Suspected, Unexpected, Serious, Adverse Reaction (SUSAR) (ie, reasonable possibility; see Section 7.1.4), Global Patient Safety and Pharmacovigilance may independently request that the treatment code be revealed (on a case-by-case basis) to comply with regulatory requirements. If this occurs, the investigator will remain blinded to treatment.

As of 10 January 2016, treatment with laquinimod was discontinued for all patients in the 1.5 mg dose group; all these discontinued patients have been unblinded. No attempts will be made to re-randomize patients whose 1.5 mg treatment was stopped to a lower dose of laquinimod.

However, the blinding was maintained for the patients in the remaining ongoing 3 treatment arms (0.5 mg/day, 1.0 mg/day, and placebo).

